10.2.2. Subject withdrawal from study vaccines

A ‘withdrawal’ from the study vaccines refers to any subject who does not receive the complete treatment, i.e. when no further planned dose is administered from the date of withdrawal. A subject withdrawn from the study vaccines may not necessarily be withdrawn from the study as further study procedures or follow-up may be performed (safety or immunogenicity *according to protocol procedure*. (Amended 27 March 2019)

Information relative to premature discontinuation of the study vaccines will be documented on the Vaccine Administration screen of the eCRF. The investigator will document whether the decision to discontinue further vaccination/treatment was made by the subject himself/herself or by the investigator, as well as which of the following possible reasons was responsible for withdrawal:

- Serious adverse event.
- Unsolicited non-serious adverse event.
- Solicited adverse event
- Not willing to be vaccinated
- Other (specify).

10.3. Extension study

During the study conclusion visit, the investigator will ask each subject if they are interested to participate in an extension study, if planned. If a subject is not interested in participating in an extension study the reason for refusal will be documented in the subject’s eCRF.

10.4. Screening failures

Screening failures are defined as subjects who are withdrawn from the study after giving informed consent, but who do not meet the inclusion and exclusion criteria.

The following information will be collected for screening failures:

- Informed consent.
- Demographic data.
- Inclusion/exclusion criteria.
- SAEs related to study participation that occurred after signing informed consent.
- Screening conclusion.

11. STATISTICAL METHODS

11.1. Primary endpoint

- Rate of moderate and severe AECOPD (any cause), occurring within a period starting 1 month post-Dose 2 and lasting for 1 year.

11.2. Secondary endpoints

Safety:

- Occurrence of each solicited local AE, during the 7-day follow-up period (Day 1 - Day 7) following each vaccination.
- Occurrence of each solicited general AE, during the 7-day follow-up period (Day 1 - Day 7) following each vaccination.
- Occurrence of any unsolicited AE, during the 30-day follow-up period (Day 1 - Day 30) following each vaccination.
- Occurrence of any pIMD from first vaccination up to study conclusion.
- Occurrence of any SAE from first vaccination up to study conclusion.

Efficacy: All AECOPD

- Yearly rate of all AECOPD (any cause, any severity) starting 1 month post-Dose 2, in vaccinated and control subjects.
 - Rate of moderate and severe AECOPD cases in vaccinated and control subjects, during 3, 6 and 9 months observation starting 1 month post-Dose 2.
 - Rate of all AECOPD cases in vaccinated and control subjects, during 3, 6, 9 and 12 months observation starting 1 month post-Dose 2.
 - Rate of all AECOPD cases in vaccinated and control subjects, during 3, 6, 9 and 12 months observation starting 1 month post-Dose 2, by severity.
- Time to first moderate or severe AECOPD.
- Time to first AECOPD of any severity.
- Time to first AECOPD, by severity.
- Duration of moderate and severe AECOPDs.
- Duration of AECOPDs of any severity.
- Duration of AECOPDs, by severity.

Efficacy: AECOPD associated to bacteriological pathogens (PCR)

- Rate of NTHi-associated and/ or Mcat-associated moderate and severe AECOPD, over a period starting 1 month post-Dose 2 and lasting for 1 year.
- Rate of NTHi-associated and/ or Mcat-associated any severity AECOPD, over a period starting 1 month post-Dose 2 and lasting for 1 year.
- Rate of NTHi-associated and/ or Mcat-associated AECOPD, over a period starting 1 month post-Dose 2 and lasting for 1 year, by severity.
- Time to first moderate or severe NTHi-associated and/ or Mcat-associated AECOPD.
- Time to first NTHi-associated and/or Mcat-associated AECOPD of any severity.
- Time to first NTHi-associated and/or Mcat-associated AECOPD, by severity.
- Duration of moderate and severe NTHi-associated and Mcat-associated AECOPD.
- Duration of NTHi-associated and/or Mcat-associated AECOPDs of any severity.
- Duration of NTHi-associated and/or Mcat-associated AECOPD, by severity.

Immunogenicity and CMI:

- Anti-PD, anti-PE, anti-PilA and anti-UspA2 total IgG antibody concentrations as measured by ELISA at Day 1, Day 31, Day 61, Day 91, Day 271 and at Day 451, in all subjects.
- NTHi-specific and Mcat- specific cell-mediated immune responses as measured by flow cytometry ICS (frequency of specific CD4⁺ T-cells expressing two or more markers, such as interleukin (IL)-2, IL-13, IL-17, interferon gamma (IFN- γ), tumour necrosis factor alpha (TNF- α), and CD40 ligand (CD40L) at Day 1, Day 91, Day 271 and at Day 451, in a sub-cohort of subjects.

11.3. Tertiary endpoints**Sputum sample PCR:**

- Occurrence (presence and absence), ***acquisition, apparition***, and bacterial load measured by PCR of NTHi and/or Mcat in sputum before first vaccination and at Day 91, Day 181, Day 271, Day 361 and Day 451 and at each AECOPD visit.
(Amended 27 March 2019)

Sputum sample culture:

- Occurrence (presence and absence), ***acquisition, apparition***, and semi-quantitative bacterial load measured in a subset of sputum sample by culture of NTHi and/or Mcat in sputum before first vaccination and at Day 91, Day 181, Day 271, Day 361 and Day 451 and at each AECOPD visit. **(Amended 27 March 2019)**
- Rate of NTHi-associated and Mcat-associated, moderate and severe AECOPD.
- Rate of NTHi-associated and Mcat-associated any severity AECOPD.

- Rate of NTHi-associated and Mcat-associated AECOPD, by severity.
- Time to first moderate or severe NTHi-associated and/or Mcat-associated AECOPD.
- Time to first any NTHi-associated and rate Mcat-associated AECOPD.
- Time to first NTHi-associated and rate Mcat-associated AECOPD, by severity.
- Duration of each moderate and severe NTHi-associated and Mcat-associated AECOPD.
- Duration of NTHi-associated and/or Mcat-associated AECOPDs of any severity.
- Duration of NTHi-associated and/or Mcat-associated AECOPD, by severity.

QOL:

- Assessment of EXACT-PRO score, daily in the evening throughout the study, in all subjects.
- Assessment of CAT score at Screening, Day 271 and Day 451, and from first vaccination to study conclusion for each AECOPD visit, in all subjects.
- Assessment of SGRQ-C score at Screening, Day 271 and Day 451, and from first vaccination to study conclusion for each AECOPD visit, in all subjects.
- Assessment of use of medication to treat (AE)COPD and healthcare utilization in all subjects throughout the study period.

Lung function:

- Assessment of FEV1% of predicted normal value at Screening, Day 271 and Day 451, in all subjects.

Biomarkers:

- Concentration of selected biomarkers (fibrinogen, hsCRP and IP-10), at Day 1 and Day 451, and for each AECOPD visit from first vaccination to study conclusion.

CMI:

- T helper profile of the specific CD4⁺ (CD8⁺) T cell response based on the expression of T helper 1, T helper 2 and T helper 17 specific markers at Day 1, Day 91, Day 271 and Day 451.

Assay development, microbiome analysis and lung inflammation:

- Presence of respiratory viral pathogens in sputum (including respiratory syncytial virus, parainfluenza virus, enterovirus/ rhinovirus, metapneumovirus, influenza virus, adenovirus, bocavirus and coronavirus) at Day 1, Day 91, Day 181, Day 271, Day 361, Day 451 and at each AECOPD visit from first vaccination to study conclusion.
- Presence and/or concentration of inflammatory cytokines in sputum at Day 1, Day 91, Day 181, Day 271, Day 361, Day 451 and at each AECOPD visit from first vaccination to study conclusion on a subset of samples.

11.4. Determination of sample size

Primary objective - Efficacy: All (causes) of moderate and severe AECOPD

The primary objective of this study is to assess the efficacy of the investigational vaccine as compared to placebo control, as measured by the rate of moderate and severe AECOPD from 1 month after second dose of vaccination till 1 year after. Sample size is computed based on the probability to detect a clinically relevant effect. Sample size is estimated using a formula from [Keen, 2007]. Assuming a yearly incidence rate of moderate and severe AECOPD in the placebo arm equal to 0.8 per subject [Mackay, 2012; Dransfield, 2013] and an over-dispersion parameter of 1.8, ~300 subjects per group will provide 80% power to detect at least a 28% reduction in the rate of AECOPDs in the vaccinated group compared to the placebo group, with a 1-sided 6.5% significance level and a dropout rate of 15%.

Table 23 presents sample size under different assumption for over-dispersion parameter and AECOPD incidence rate in placebo arm, assuming a VE=28%, a drop-out of 15% (85% of enrolled subjects are expected to complete one year follow up) and 1:1 randomization ratio.

Table 23 Total number of subjects for primary endpoint

Overdispersion factor*: 1.8				
2-side α -level	Rate in Placebo	Rate in Treatment	N per group	Total Sample size**
13%	0.9	0.648	228	536
10%	0.9	0.648	254	596
13%	0.8	0.576	257	604
10%	0.8	0.576	286	672
13%	0.7	0.504	293	690
10%	0.7	0.504	327	768
13%	0.6	0.432	342	804
10%	0.6	0.432	381	896
Overdispersion factor*: 2				
13%	0.9	0.648	251	590
10%	0.9	0.648	280	658
13%	0.8	0.576	282	664
10%	0.8	0.576	314	740
13%	0.7	0.504	323	760
10%	0.7	0.504	360	846
13%	0.6	0.432	376	886
10%	0.6	0.432	419	986

Sample size calculated from a formula from Keen, 2007 implemented on SAS.

* Overdispersion factor for a Poisson distribution.

**Total sample size takes in to account 15% drop-out rate.

Secondary objective - Efficacy: mild and moderate AECOPD associated to bacteriological pathogens (PCR).

One of the secondary objectives is to assess efficacy of the investigational vaccine compared to placebo, as measured by the rate of moderate and severe AECOPD associated to NTHi and/or Mcat (detected by PCR), starting from 1 month after second dose of vaccination till 1 year after.

Assuming an incidence rate of AECOPD (all causes) equal to 0.8 per subject per year, a vaccine efficacy of 70% against AECOPD associated with NTHi and/or Mcat and assuming that 25% of AECOPDs are associated with NTHi and 15% with Mcat [Wang, 2015; Garcha, 2012], Table 24 shows the sample size requested for the bacteriological endpoint, assuming a rate of loss sputum samples equal to 20%.

Table 24 Sample size for secondary bacteriological endpoint

All AECOPD Rate	NTHi	Mcat	2-side α-level	Beta	N per group	Sample** size
0.8	20%	10%	13%	0.2	308	908
0.8	25%	15%	13%	0.2	218	642
0.8	20%	10%	10%	0.2	339	998
0.8	25%	15%	10%	0.2	237	694
0.8	20%	10%	13%	0.3	248	730
0.8	25%	15%	13%	0.3	175	514
0.8	20%	10%	10%	0.3	276	810
0.8	25%	15%	10%	0.3	196	578

Sample size calculated from a formula from Keen, 2007 implemented on SAS.

**Total sample size takes in to account for 15% of subject drop-out and 20% of samples lost.

Study is planned to enrol approximately 600 subjects (~300 in each arm), assuming a subject drop-out rate of 15% and a loss of sputum samples of 20%, we have a power of 77.5% to detect a reduction in AECOPDs associated with NTHi and/or Mcat of at least 70% of vaccine efficacy with a 1-sided 6.5% significance level.

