Similarly, VE in prevention of NTHi and/or Mcat associated AECOPD, over a period starting 1 month post-Dose 2 and lasting for 1 year and its 95% CI will be computed, with the following incidence rate:

- NTHi-associated moderate and severe AECOPD.
- NTHi-associated all-severity AECOPD.
- NTHi-associated AECOPD, by severity.
- Mcat-associated moderate and severe AECOPD.
- Mcat-associated all-severity AECOPD.
- Mcat-associated AECOPD, by severity.
- NTHi and/or Mcat-associated moderate and severe AECOPD.
- NTHi and/or Mcat-associated all-severity AECOPD.
- NTHi and/or Mcat-associated AECOPD, by severity.
- The time until first moderate and severe AECOPD.
- The time until first AECOPD (any severity).
- The time until first AECOPD by severity.

The proportion of sputum samples with exact 95% CI obtained at each visit (scheduled visits and AECOPD-driven visits) and positive for bacterial pathogens (overall and by bacterial pathogen) will be computed by group and overall. The exact CIs will be estimated assuming independence of bacterial results across sputum samples.

Incidence rates of AECOPD associated to NTHi and/or Mcat, and VE, together with 95% CI will be evaluated for the following time periods:

- At Month 3, 6, 9, 12, 15 from day 1 (cumulative)
- At 6 months follow up period (from 1 month post-Dose 2)
- At 3 months follow up period (from 1 month post-Dose 2)

The model used will be the same as for the primary analysis. All above analyses will be performed in sputum samples using PCR. (Amended 27 March 2019)

Efficacy – Bacteriological Endpoint (culture)

Same set of analyses, as in the bacteriological efficacy endpoints, will be performed in the subset of culture sputum data.

Incidence rates of AECOPD associated to NTHi and/or Mcat, and VE, together with 95% CI will be evaluated for the following time periods:

- At Month 3, 6, 9, 12, 15 from day 1 (cumulative)
- At 6 months follow up period (from 1 month post-Dose 2)
- At 3 months follow up period (from 1 month post-Dose 2)

The model used will be the same as for the primary analysis. All above analyses will be performed in sputum samples using PCR. (Amended 27 March 2019)

Bacteriological load

The following will be performed in PCR and culture samples:

- Percentage of subjects with *H. influenzae* and *M. catarrhalis* in sputum before first vaccination and at Day 91, Day 181, Day 271, Day 361 and Day 451, per group.

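### Table 24 and the 77.5% power in Section 11.4 do not belong to the NTHi and/or Mcat composite to which the text assigns them

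*Protocol*

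**What the plan says.** Protocol Section 11.4 describes the secondary endpoint "as measured by the rate of moderate and severe AECOPD associated to NTHi and/or Mcat (detected by PCR"), counted over the year that starts one month after Dose 2. The inputs are 0.8 all-cause events per subject-year on placebo, 70% efficacy on the pathogen-related events, and these pathogen shares: "assuming that 25% of AECOPDs are associated with NTHi and 15% with Mcat".

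For the 25%/15% scenario at two-sided 13% and 80% power, Table 24 gives 218 per group, or 642 in total after 15% drop-out and 20% lost sputum samples. The closing sentence then says that with about 300 per arm "we have a power of 77.5% to detect a reduction in AECOPDs associated with NTHi and/or Mcat of at least 70% of vaccine efficacy", at a one-sided 6.5% level. Tables 23 and 24 cite the same formula source. Table 23 shows its over-dispersion (1.8 or 2); Table 24 shows none. The text gives no overlap between the two pathogens, and nothing in it says that each pathogen must be shown separately.

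The sub-heading reads "mild and moderate AECOPD associated to bacteriological pathogens (PCR"), while the paragraph below it refers to moderate and severe events. For the PCR endpoint, Section 11.8 says that vaccine efficacy over the period "lasting for 1 year and its 95% CI will be computed"; the 87% interval is reserved for the primary endpoint.

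**The concern.** At 70% efficacy on a placebo rate of 0.8 x 0.40 = 0.32 per year, 204 evaluable subjects per arm would have about 204 x 0.32 = 65 events against 204 x 0.096 = 20. A contrast of that size should not have only 77.5% power, nor need 218 per group for 80%.

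The endpoint is the one closest to the vaccine's mechanism in a proof-of-concept trial, so the stated power affects how a null result is read. As printed, a null composite result at a true efficacy of 70% looks like a miss with a chance of 22.5%. For the composite, the chance is much smaller. If separate success on both pathogens was meant, the text names the wrong criterion, and the power at the confidence level reported is well below 77.5%. The two readings point in opposite directions.

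**Working it through.** **Formula.** N per group = (z_a + z_b)^2 x [1/m0 + 1/m1 + 2k] / ln(m1/m0)^2, where m0 and m1 are the placebo and vaccine rates and k = (over-dispersion - 1)/m0. Power = Phi(sqrt(N x ln(m1/m0)^2 / [1/m0 + 1/m1 + 2k]) - z_a). At two-sided 13% and 80% power, (1.514 + 0.842)^2 = 5.55.

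**Step 1: reproduce Table 23.** With m0 = 0.8, m1 = 0.576 and over-dispersion 1.8: 5.55 x (1.25 + 1.736 + 2)/0.1079 = 256.4, against the printed 257. All 16 rows agree to within one subject (for example 341.9 against 342, and 419.1 against 419).

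**Step 2: evaluable numbers.** 300 x 0.85 x 0.80 = 204 per group. The same factor recovers the printed total: 218/0.68 = 320.6, rounded up to 321, and doubled is 642.

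**Step 3: the composite as named.** With m0 = 0.32, m1 = 0.32 x 0.30 = 0.096 and over-dispersion 1.8, k = 2.5: 5.55 x (3.125 + 10.417 + 5)/1.4496 = 71, against the printed 218. Power at 204 is Phi(3.994 - 1.514) = 99.3% at two-sided 13%, and Phi(3.994 - 1.960) = 97.9% at 5%.

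**Step 4: vary what the protocol does not state.** Over-dispersion is taken as 1.8 to 2.0, from Table 23. Overlap ranges from none (25% + 15% = 40%), through independence (0.25 + 0.15 - 0.25 x 0.15 = 36.25%), to Mcat wholly nested in NTHi (25%). In each pair the first figure is for 1.8 and the second for 2.0.

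| Share of AECOPD | N per group, 80% power, 13% | Power at 204, 13% | Power at 204, 5% |
|---|---|---|---|
| 40% | 71 / 76 | 99.3% / 99.1% | 97.9% / 97.2% |
| 36.25% | 78 / 84 | 98.9% / 98.5% | 96.7% / 95.7% |
| 25% | 114 / 121 | 95.0% / 93.8% | 88.4% / 86.3% |
| Protocol | 218 | 77.5% | not given |

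To need 218 for the additive composite, the over-dispersion would have to be about 7.9, or the efficacy about 45% instead of 70%.

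**Step 5: a calculation that comes close.** Take NTHi alone (0.20 against 0.06) and Mcat alone (0.12 against 0.036), require success on both, and treat the two as independent. At 204 per group:

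- Over-dispersion 1.8: 0.950 x 0.824 = 78.3% at 13%; 0.884 x 0.686 = 60.7% at 5%.
- Over-dispersion 2.0: 75.4% at 13%; 56.8% at 5%.

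The N for 80% joint power at 13% is 212 (1.8) to 227 (2.0), which brackets 218. Across the eight rows, joint N at 1.8 is 304/212/335/234/241/171/269/190, against the printed 308/218/339/237/248/175/276/196. That is 1% to 3% low in every row. At 2.0 it is 3% to 6% high in every row.

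**The case against.** The strongest reply is that little depends on these figures. Section 11.11 makes secondary comparisons descriptive, the only success rule in Section 11.8 is for the primary endpoint, and enrolment of about 600 rests on the primary calculation (Table 23: 604). For the endpoint as named, the error is conservative. All of this stands. It limits the seriousness of the point but does not make the printed power right.

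A second reply is that exact replacement values cannot be derived from the protocol, because Table 24 gives no over-dispersion and no overlap. That also stands, so ranges are shown. The primary efficacy of 28% = 0.40 x 0.70 is consistent with simple addition of the shares, but the protocol does not say that it was derived that way.

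Two stronger readings are tempting. A reader might infer that the chance of missing a true 70% effect on the composite is below 1%. That holds only at the 13% level with no overlap; at the 95% level reported it is about 2% to 3% with additive shares, 3% to 4% with independent overlap, and 12% to 14% with full nesting. A reader might also infer that Table 24 was certainly computed for success on both pathogens. The agreement is close but not exact, unlike the fit to Table 23, so this remains an inference.

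The sub-heading's severity wording is a clerical slip. Quoting power at 13% beside 95% intervals is a minor mismatch, since Appendix D shows that the 87% interval was removed from secondary analyses on purpose.

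**Conclusion.** The point holds: the figures are wrong as written for the endpoint named. No overlap of the two pathogens combined with an over-dispersion of 1.8 to 2.0 brings the composite near 218 per group or 77.5% power. The required N is 71 to 121, and power at 204 per group is 94% to 99% at two-sided 13% and 86% to 98% at the 95% confidence level. This rests on the formula calibrated on Table 23 and on carrying that table's over-dispersion over to Table 24.

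It should be corrected but is not critical. The documents do not support a claim that the composite is underpowered, that the sample size is wrong, or that the primary analysis is affected. Only if separate success on both pathogens was the real aim is power a concern, at about 57% to 61% with 95% intervals.

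**What to change.** State in Section 11.4 which endpoint Table 24 and the power sentence describe.

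- If it is the composite, recompute Table 24 and restate the power, giving the over-dispersion and the pathogen overlap assumed.
- If it is separate success on NTHi and on Mcat, replace *and/or* in the power sentence, say that both are required, and state the over-dispersion.

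In either case, give the power also at the 95% confidence level used in Section 11.8, and align the severity wording of the sub-heading with the paragraph below it. The cost is a text and table correction; enrolment stays at about 600 and the analysis is unchanged.

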11.8. Analysis of efficacy

The primary analysis will be performed on the mTVC and repeated on the TVC **and the FAS**. The primary analysis will also be repeated on the efficacy ATP (per-protocol) cohort if the percentage of vaccinated subjects excluded from the ATP cohort for efficacy is more than 5%.

Efficacy – Clinical Endpoint

The following incidence rates of AECOPD (any type) occurring from enrolment up to 1 month post-Dose 2 will be computed together with **95% CI**, and incidence rates together with VE in the prevention of AECOPD (any type) will be computed over a period starting 1 month post-Dose 2 and lasting for 1 year, with **95% CI**:

- All-cause moderate and severe AECOPD (primary endpoint).
- All-cause, all-severity AECOPD.
- All-cause AECOPD, by severity.

For the primary endpoint, the 87% CI will also be reported in order to evaluate the null hypothesis at 13% alpha level (2-side). This objective will be considered a success if the lower limit of the 87% CI will be above 0%. (Amended 27 March 2019)

The CIs of the incidence rate will be computed using a model which accounts for repeated events. The primary outcome will be analysed using the Negative Binomial regression model with number of AECOPD as dependent variable; treatment (vaccine or placebo), age group (40–59 years or 60–80 years), GOLD grade (2, 3 or 4), history of exacerbations (<2 or ≥ 2) and country as independent variables, with logarithm as link function, and the logarithm of time for follow-up (in years) as an offset variable. If the model does not converge, the Poisson distribution will be used instead of the Negative Binomial one.

VE for AECOPD events is defined as:

$$VE(\text{AECOPD}) = 1 - R_{\text{vacc}} / R_{\text{con}}$$

with:

- R_{vacc} = average yearly incidence rate of AECOPD events per subject in the group 10-10-3-AS.
- R_{con} = average yearly incidence rate of AECOPD events per subject in the Control group.

Incidence rates of AECOPD (any type) and VE, together with 95% CI, will be computed for the following time periods:

- At Month 3, 6, 9, 12, 15 from Day 1 (cumulative)
- By 6 Months follow up period (from 1 month post-Dose 2)
- By 3 Months follow up period (from 1 month post-Dose 2)

The model used will be the same as for the primary analysis.

A sensitivity analysis **using** a permutation test will be performed for the primary efficacy endpoint.

Efficacy – Bacteriological Endpoint (PCR)

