11.11. Interpretation of analyses

The primary objective of this POC will be evaluated at alpha error of 13% (two-sided test) which is the measurement of the accuracy of our estimation.

Comparative analyses related to the secondary and tertiary objectives, with the aim to characterise the difference in reactogenicity/ immunogenicity/ efficacy between groups will be descriptive and should be interpreted with caution.

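### The 77.5% power for the NTHi/Mcat endpoint is stated at a two-sided 13% level, but only a 95% CI is planned for that endpoint

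*Protocol*

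**What the plan says.** Section 11.4 makes an explicit power claim for the secondary bacteriological endpoint: "we have a power of 77.5% to detect a reduction in AECOPDs associated with NTHi and/or Mcat", completed by the effect size and level in "reduction in AECOPDs associated with NTHi and/or Mcat of at least 70% of vaccine efficacy with a 1-sided 6.5% significance level". One-sided 6.5% is two-sided 13%. Every row of Table 24 uses 13% or 10% two-sided; none uses 5%.

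For the PCR-based bacteriological endpoint, Section 11.8 plans vaccine efficacy "over a period starting 1 month post-Dose 2 and lasting for 1 year and its 95% CI will be computed". The analyses by time period also carry 95% CIs. The wider interval is tied to one endpoint only: "For the primary endpoint, the 87% CI will also be reported in order to evaluate the null hypothesis at 13% alpha level (2-side". Section 11.11 agrees: "The primary objective of this POC will be evaluated at alpha error of 13% (two-sided test". The same section calls the comparisons for secondary and tertiary objectives descriptive and asks for cautious reading.

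**The concern.** A power figure has meaning only relative to a level. The level behind the 77.5% is used nowhere in the planned analysis of this endpoint. The only interval a reader of the results will see is the 95% CI, and 77.5% will naturally be taken as the chance that this interval excludes 0% when true efficacy is 70%.

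This endpoint is the pathogen-specific support for the proof of concept. A reader who believes an inconclusive interval had a 22.5% chance under 70% efficacy will treat one as stronger evidence against a pathogen-specific effect than it is.

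**Working it through.** **Inputs from Section 11.4**
- Sample: "Study is planned to enrol approximately 600 subjects (~300 in each arm), assuming a subject drop-out rate of 15% and a loss of sputum samples"; the second loss is put at 20%. Evaluable per arm: 300 × 0.85 × 0.80 = 204.
- Rate: "Assuming an incidence rate of AECOPD (all causes) equal to 0.8 per subject per year".
- Effect: "a vaccine efficacy of 70% against AECOPD associated with NTHi and/or Mcat", so the rate ratio is 0.30, |ln 0.30| = 1.204.
- Pathogen shares: NTHi 25% and Mcat 15%, giving placebo rates 0.8 × 0.25 = 0.20 and 0.8 × 0.15 = 0.12 per year.
- Over-dispersion: 1.8, stated for the primary endpoint. None is stated for this endpoint, so carrying 1.8 over is an assumption.

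**Step 1. Formula check on the primary endpoint.** With control and vaccine rates m0 and m1:

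n = (zα + zβ)² × (1/m0 + 1/m1 + 2k) / ln(RR)², k = (φ − 1)/m0.

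For rates 0.8 and 0.576 at 13%: (1.514 + 0.842)² × (1.25 + 1.736 + 2) / 0.1079 = 256.4, against 257 printed. All 16 rows of Table 23 are reproduced within 1 subject.

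**Step 2. Reproduce the bacteriological figure.** The same formula is applied to NTHi and Mcat separately and the two powers are multiplied. This comes within about 3% of the N per group in all eight rows of Table 24, always slightly below (for example 304 against 308, 213 against 218, 171 against 175, 190 against 196).

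Power = Φ(√204 × 1.204 / √V − zα), with V = 1/m0 + 1/m1 + 2k:
- NTHi: V = 5 + 16.67 + 8 = 29.67; non-centrality 3.157.
- Mcat: V = 8.33 + 27.78 + 13.33 = 49.44; non-centrality 2.446.

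| Two-sided level | zα | NTHi | Mcat | Both (product) |
|---|---|---|---|---|
| 13% | 1.514 | 95.0% | 82.4% | 78.3% |
| 5% | 1.960 | 88.4% | 68.6% | 60.7% |

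The 78.3% at 13% compares with 77.5% printed, so the protocol's figure is reproduced to within a point at its own level.

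**Step 3. Move the printed figure to 5% without the reconstruction.** Treat 77.5% as the power of one Wald-type test: the non-centrality is 1.514 + 0.755 = 2.270, and Φ(2.270 − 1.960) = 62.2%. No dispersion assumption enters.

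**Step 4. Variants at two-sided 5%**
- Scaling the Table 24 row for 80% power (218 per group, 13%) to 204: 62.5%.
- Scaling the row for 70% power (175 per group, 13%) to 204: 59.5%.
- Setting φ to 1.853, so that Step 2 gives exactly 77.5% at 13%: 59.6%.

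The range is 59.5–62.5%. A different dispersion convention, k = 0.8/0.8 = 1 for both pathogens, would give 75.0% at 5%. It does not fit Table 24, however: it needs 166 per group where 218 is printed.

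**Step 5. The single combined rate.** With no overlap between pathogens the placebo rate is 0.8 × 0.40 = 0.32. With overlap of 5 or 10 percentage points it is 0.28 or 0.24. The formula with φ = 1.8 gives 97.9%, 96.2% and 93.3% at two-sided 5%. At 0.32 it gives 99.3% at 13%, far from 77.5%, so the printed figure was evidently not computed for that rate.

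**The case against.** The strongest reply is that nothing is miscalculated. The sentence in Section 11.4 gives its level, Table 24 has a column for it, and 77.5% reproduces there. A reader might infer an arithmetic error; the documents do not support that.

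A reader might also infer that a 5% test of this endpoint is planned and underpowered. That is not supported either. Section 11.11 makes secondary comparisons descriptive, the only success rule belongs to the primary, and a descriptive 95% CI is not a decision rule. The Amendment 1 rationale in Appendix D records that the 87% CI was kept for the primary alone because 95% CIs are underpowered in this study. The narrower role of the 95% interval was therefore deliberate, and Section 11.4 was left unaligned.

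Third, the endpoint named in Section 11.4 is the combined NTHi and/or Mcat rate. It would be wrong to say this combined endpoint has 61% power: on the same formula it has roughly 93–98%. The 61% applies only if both pathogens must succeed separately. The protocol states no such joint criterion, no independence assumption and no dispersion for this endpoint, so the reconstruction is an inference from the fit to Table 24.

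All three points stand and limit the finding. They do not remove it: the protocol fixes both a power figure and an interval for this endpoint, at different levels.

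**Conclusion.** The inconsistency is real and rests on current text. The 77.5% in Section 11.4 is correct at two-sided 13% but corresponds to no analysis that Sections 11.8 and 11.11 plan for this endpoint. On the calculation behind the printed figure, the 95% CI would exclude 0% about 60–62% of the time at 70% efficacy. An interval including 0% would then be expected about 38–40% of the time rather than 22.5%.

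The 62.2% shift assumes only that 77.5% is the power of one Wald-type test. The 60.7% (NTHi 88%, Mcat 69%) also assumes a joint criterion, independent tests and dispersion 1.8. The effect is on how the result is read; no planned analysis or decision rule is affected.

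**What to change.** In Section 11.4, restate the bacteriological power at the two-sided 5% level that matches the 95% CI, rerun with the sponsor's own program, and add 5% rows to Table 24. State which endpoint and dispersion each figure assumes. As a guide, on the assumptions above: about 61% if NTHi and Mcat must both succeed (about 88% and 69% separately), against roughly 93–98% for the single combined rate at 0.24–0.32 per year. These are approximations to be replaced by the sponsor's own output.

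Alternatively, also report an 87% CI for this endpoint in Section 11.8, so that the existing power statement has an interval it describes.

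The cost is wording and a recalculated table, or one extra interval in the report. No further patients or data are needed. The downside of the first option is a less favourable stated power for a secondary endpoint, if the joint calculation is kept.
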